6.1 Treating the patient

The treating investigator needs to instruct the patient to take the study drug as per protocol. All dosages prescribed and dispensed to the patient and any dose change or interruption must be recorded appropriately.

6.1.1 Administration

BGJ398 (infigratinib) will be taken once daily on a three weeks on, one week off schedule. BGJ398 (infigratinib) will be dosed orally on a flat dosing scale of 125 mg/day, irrespective of size and weight.

Table 6-1 Treatment and treatment schedule

Study treatments	Pharmaceutical form and route of administration	Dose	Frequency and/or regimen
BGJ398 (infigratinib)	Capsule for oral use	125mg (administered as one 100 mg capsule and one 25 mg capsule)	Daily (3 weeks on, 1 week off in a 28 day cycles)

6.1.2 Instructions for Administration of BGJ398 (infigratinib)

The following general guidelines should be followed for BGJ398 (infigratinib) administration:

- Patients should be instructed to take the daily dose of BGJ398 (infigratinib) in the morning, at approximately the same time each day (24 ± 2 hr interval).
- BGJ398 (infigratinib) should be administered in the fasted state, at least 1 hour before or 2 hours after a meal.
- Phosphate binders should be given with meal (low phosphate diet), every day on days BGJ398 (infigratinib) is given. No treatment with phosphate binders is needed during the BGJ398 (infigratinib) off week in a cycle, unless the lab results indicate higher serum phosphorus levels that require continuous treatment with phosphate binders.
- BGJ398 (infigratinib) should be taken with a large glass of water (~250 mL) and consumed over as short a time as possible. Patients should be instructed to swallow the capsules whole and not chew them.
- If the patient forgets to take the scheduled dose in the morning, he/she should not take the dose more than 2 hours after the usual time and should continue treatment the next day. Any doses that are missed should be skipped altogether and should not be replaced or made up at the next scheduled dosing.
- If vomiting occurs following the dosing of study drug, re-dosing is not permitted that same day. Dosing should resume the next day.

- BGJ398 (infigratinib) is characterized by pH-dependent solubility, and therefore, medicinal products that alter the pH of the upper gastro-intestinal tract may alter the solubility of both compounds, and limit bioavailability. These agents include, but are not limited to, proton-pump inhibitors (e.g., omeprazole), H₂-antagonists (e.g., ranitidine) and antacids. Therefore, BGJ398 (infigratinib) should be dosed at least 2 hours before or 10 hours after dosing with a gastric protection agent.
- Patients must avoid consumption of grapefruit, pomelos, pomegranates, star fruits, Seville oranges or products containing the juice of each during the entire study and preferably 7 days before the first dose of study medications, due to potential CYP3A4 interaction with the study medications. Orange juice is allowed.
- Patients on strong or moderate CYP3A4 inducers or inhibitors or medications that rely on CYP3A4 for metabolism, should switch whenever possible to a product with less interaction with/reliance on the pathway or patient should be on a stable dose of the medication prior to enrollment

6.1.3 Ancillary treatments with anti-emetics, phosphate lowering agents, anti-diarrheals, and growth factors

Anti-emetics

Anti-emetics are allowed for the treatment of nausea or vomiting. It is recommended to avoid using drugs that are known to cause QT prolongation. Note that some anti-emetics have a known risk for Torsade de Pointes, and therefore need to be used with caution. Aprepitant is both a sensitive substrate and a moderate CYP3A4 inhibitor and can be used with caution if an alternative is not available.

Phosphate-lowering therapy

Phosphate-lowering treatment, including low phosphate diet and phosphate binding therapy, such as sevelamer hydrochloride, should be implemented prophylactically at study drug initiation and modified as clinically indicated throughout BGJ398 (infigratinib) administration

Anti-diarrheals

No prophylactic anti-diarrhea therapy is recommended. However, patients should have loperamide tablets at home in case BGJ398 (infigratinib) induced diarrhea occurs and should call the study doctor or study staff at the first onset of loose stools. Patients should also be instructed to record the number of stools and report severe symptoms (e.g., fever or dizziness on standing). Initial management of mild to moderate diarrhea should include dietary modifications (e.g., eliminating all lactose-containing products and high-osmolar dietary supplements), extra fluids to prevent dehydration and loperamide at an initial dose of 4mg followed by 2 mg every 4 hours or after every unformed stool but not to exceed 16 mg/day.

In case of persistent, (i.e. >48 hrs on loperamide), or aggravated diarrhea, the patient should be seen at the investigational site or in the physician's office/outpatient center for further evaluation, including complete stool and blood work-up and intensified anti-diarrhea treatment per institutional guidelines.

Hematopoietic growth factors

Prophylactic use of recombinant hematopoietic growth factors (e.g., G-CSF and related analogues, erythropoietin alfa and related analogues) should not be used during cycle 1. However, they are allowed during future cycles for prophylaxis of neutropenia and treatment of anemia if deemed medically appropriate or if, in the opinion of the treating investigator, failure to do so could compromise the patient's ability to remain in the study. Patients receiving erythropoietin alfa or related analogues at time of enrollment may continue therapy with initiation of cycle 1 of treatment.

6.1.4 Dosing and treatment schedule

BGJ398 (infigratinib) will be dosed at 125 mg PO daily with three weeks on therapy, and one week off therapy. Dosing information will be captured per cycle given the mandated off week. There is no dose escalation. Dose is the established phase II dose.

6.1.5 Dose modification and dose delay

For patients who do not tolerate the protocol-specified dosing schedule, dose adjustments are permitted in order to allow the patient to continue the study treatment. The following guidelines need to be applied:

These changes must be recorded appropriately.

All dose modifications should be based on the worst preceding toxicity.

Following resolution of toxicity to baseline or \leq grade 1, treatment is resumed at either the same or lower doses of study drugs as per the criteria in [Table 6-3](#). If treatment is resumed at the same doses of study drugs, and the same toxicity recurs with the same or worse severity regardless of duration, doses must be reduced to the next lower dose level. If treatment is resumed at the lower doses of study drugs, and the same toxicity recurs with the same or worse severity, the patient must discontinue study treatment.

If a patient requires a dose delay of > 14 consecutive days of BGJ398 (infigratinib) from the intended day of the next scheduled dose, then the patient should be discontinued from the study treatment, unless extenuating circumstance occur and approval from Novartis is obtained.

Patients who discontinue the study for a study related adverse event or an abnormal laboratory value must be followed as described in [Section 6.1.5](#).

Table 6-2 Dose reduction table

Dose reduction			
	Starting dose level 0	Dose level - 1	Dose level - 2
BJG398	125 mg	100 mg	75 mg

A third or subsequent reduction (to 50 mg) in dose may be allowed if the patient is clearly benefiting from study treatment (i.e., stable disease, partial response, or complete response) but is experiencing adverse events that prevent continued treatment at the already reduced dose.

Table 6-3 Recommended dose modifications for BGJ398 (infigratinib) treatment

6.2 Worst Toxicity CTCAE v4.03 Grade (unless otherwise specified)	6.3 Recommended Dose Modifications any time during a cycle of therapy
Cardiac disorders	
Cardiac - Prolonged QTcF interval	
Grade 1 and 2 : QTcF \geq 481msec and \leq 500 msec (asymptomatic)	
Maintain dose level of BGJ398 (infigratinib) ECG assessments should be performed for 2 additional cycles at the same frequency as in cycle 1, or as clinically indicated
 
 If ECG assessments show no QTcF \geq 481 msec, for subsequent cycles ECG monitoring will be performed as per visit schedule. If ECG assessments are still abnormal (QTcF \geq 481 msec and \leq500 msec), then ECG monitoring must continue at the same frequency as in cycle 1 for all subsequent cycles.
Grade 3 : QTcF > 500msec as identified on the ECG by the investigator	
 Hold BGJ398 (infigratinib). Monitor patient with hourly ECGs until the QTcF has returned to baseline. Perform further monitoring as clinically indicated. Exclude other causes of QTcF prolongation such as hypokalemia, hypomagnesaemia and decreased blood oxygenation. Patients should receive appropriate electrolyte replacement and should not receive further BGJ398 (infigratinib) until electrolytes are documented to be within normal limits. 
Once the QTcF prolongation has resolved and if the QTcF prolongation was confirmed by the central reader, patients may be re-treated at one lower dose level at the investigator's discretion
 
 ECG assessments should be performed for 2 additional cycles at the same frequency as in cycle 1 or as clinically indicated

6.2 Worst Toxicity CTCAE v4.03 Grade (unless otherwise specified)	6.3 Recommended Dose Modifications any time during a cycle of therapy
	
 ○ If ECG assessments show no QTcF \geq 481 msec, for subsequent cycles ECG monitoring will be performed as per visit schedule. ○ If ECG assessments are still abnormal (QTcF \geq 481 msec and \leq500 msec), then ECG monitoring must continue at the same frequency as in cycle 1 or as clinically indicated, for all subsequent cycles ● Patients who experience recurrent QTcF \geq 500msec after one dose reduction will be discontinued from study. 
NB: If ventricular arrhythmia or Torsades de Pointes is observed in a patient, he/she will be discontinued from the study.

Cardiac disorders - others Grade \geq 3, or congestive heart failure \geq 2	Discontinue patient from study treatment.
Investigations-Hematology	
ANC decreased (Neutropenia) Grade 3 (ANC $<$ 1.0 - 0.5 x 10 ⁹ /L) Grade 4 (ANC $<$ 0.5 x 10 ⁹ /L)	Hold dose of BGJ398 (infigratinib) until resolved to CTCAE Grade \leq 1 or baseline, then 
 ● If resolved in \leq 7 days, maintain dose level of BGJ398 (infigratinib) ● If resolved in $>$ 7 days, \downarrow 1 dose level of BGJ398 (infigratinib). Hold dose of BGJ398 (infigratinib) until resolved to CTCAE \leq Grade 1, \downarrow 1 dose level of BGJ398 (infigratinib).
Febrile neutropenia Grade 3 (ANC $<$ 1.0 x 10 ⁹ /L, single temperature of $>$ 38.3°C or a sustained temperature of \geq 38.0°C) Grade 4	Hold dose of BGJ398 (infigratinib) until resolved to CTCAE Grade \leq 1, then 
 ● If resolved by \leq 7 days, \downarrow 1 dose level of BGJ398 (infigratinib). ● If not resolved within 7 days discontinue patient from study drug treatment. Discontinue patient from study treatment.
Hemoglobin Grade 3 ($<$ 8.0 mg/dL – 6.5 mg/dL) Grade 4 ($<$ 6.5 mg/dL)	Hold dose of BGJ398 (infigratinib) until resolved to CTCAE Grade \leq 1 or baseline, then maintain dose level Hold dose of BGJ398 (infigratinib) until resolved to CTCAE Grade \leq 1 or baseline, then \downarrow 1 dose level

6.2 Worst Toxicity CTCAE v4.03 Grade (unless otherwise specified)	6.3 Recommended Dose Modifications any time during a cycle of therapy

Platelet count decreased (Thrombocytopenia)
 
Grade 3 (PLT < 50 - 25 x 10⁹/L) without bleeding
 
Grade 3 (PLT < 50 - 25 x 10⁹/L) with bleeding or Grade 4 (PLT < 25 x 10⁹/L)
	
Hold dose of BGJ398 (infigratinib) until resolved to CTCAE Grade ≤ 1 or baseline
 
 • If resolved in ≤ 7 days, maintain dose level of BGJ398 (infigratinib). • If resolved in > 7 days, ↓ 1 dose level of BGJ398 (infigratinib) 
Hold dose of BGJ398 (infigratinib) until resolved to CTCAE Grade ≤ 1 or baseline, then ↓ 1 dose level

Investigations – Renal	

Serum creatinine
 
Grade 1 and Pi >5.5 mg/dL and/or tCa x Pi >55 mg²/dl² and despite phosphorus lowering therapy for at least 14 days
 
Grade 2 (> 1.5 - 3.0 x ULN)
 
Grade 2 and Pi >5.5 mg/dL and/or tCa x Pi >55 mg²/dl² and despite phosphorus lowering therapy for at least 14 days
 
Grade ≥ 3 (> 3.0 x ULN)
	
Hold dose of BGJ398 (infigratinib) until resolved to CTCAE Grade ≤ 1 or baseline
 
 • If resolved in ≤ 7 days, maintain dose level of BGJ398 (infigratinib). • If resolved in > 7 days, ↓ 1 dose level of BGJ398 (infigratinib). 
Hold dose of BGJ398 (infigratinib) until resolved to CTCAE Grade ≤ 1 or baseline
 
 • If resolved in ≤ 7 days, maintain dose level of BGJ398 (infigratinib). • If resolved in > 7 days, ↓ 1 dose level of BGJ398 (infigratinib). 
Discontinue patient from study treatment
 
Discontinue patient from study treatment.

Investigations – Hepatic	

Blood bilirubin (patients with Gilbert Syndrome these dose modifications apply to changes in direct bilirubin only)
 
Grade 2 (>1.5 – 3.0 x ULN)
 
Grade ≥ 3 (> 3.0 x ULN)
	
Hold dose of BGJ398 (infigratinib) until resolved to CTCAE Grade ≤ 1
 
 • If resolved in ≤ 7 days, maintain dose level of BGJ398 (infigratinib). • If resolved in > 7 days, ↓ 1 dose level of BGJ398 (infigratinib). 
Discontinue patient from study treatment.

6.2 Worst Toxicity CTCAE v4.03 Grade (unless otherwise specified)	6.3 Recommended Dose Modifications any time during a cycle of therapy
	Note: If CTCAE Grade 3 or 4 hyperbilirubinemia is due to hemolysis, then ↓ 1 dose level of BGJ398 (infigratinib) and continue treatment at the discretion of the Investigator.

AST or ALT Grade 3 (> 5.0 - 20.0 x ULN) without bilirubin elevation > 2.0 x ULN
 
Grade 4 (> 20.0 x ULN) without bilirubin elevation > 2.0 x ULN
	
Hold dose of BGJ398 (infigratinib) until resolved to CTCAE Grade ≤ 1 or baseline
 
 • If resolved in ≤ 7 days, maintain dose level of BGJ398 (infigratinib). • If resolved in > 7 days, ↓ 1 dose level of BGJ398 (infigratinib). 
Discontinue patient from study treatment.


AST or ALT and Bilirubin AST or ALT > 3.0 – 5.0 x ULN and total bilirubin > 2.0 x ULN without liver metastasis or evidence of disease progression in the liver
 
AST or ALT > 5.0 x ULN and total bilirubin > 2.0 x ULN
	
Hold dose of BGJ398 (infigratinib) until resolved to CTCAE Grade ≤ 1
 
 • If resolved in ≤ 7 days, ↓ 1 dose level of BGJ398 (infigratinib). • If resolved in > 7 days, discontinue patient from study treatment. 
Discontinue patient from study treatment.

Laboratory / Metabolic disorders	

Asymptomatic amylase and/or lipase elevation
 
Grade 3 (> 2.0 - 5.0 x ULN)
 
Grade 4 (> 5.0 x ULN)
	
 • Hold dose of BGJ398 (infigratinib) until resolved to CTCAE Grade ≤ 2. • ↓ 1 dose level of BGJ398 (infigratinib) 
Note: A CT scan or other imaging study to assess the pancreas, liver, and gallbladder must be performed within 1 week of the first occurrence of any CTCAE ≥ Grade 3 amylase and/or lipase.
 
If asymptomatic CTCAE Grade 2 elevations of lipase and/or amylase occur again at the reduced dose, patients will be discontinued permanently from study treatment.
 
Discontinue patient from study treatment

Hyperphosphatemia Serum phosphorus > 5.5 – 7.0 mg/dL
	
Maintain dose level of BGJ398 (infigratinib), but modify phosphate lowering therapy
 
Hold BGJ398 (infigratinib) dose until resolved to serum phosphorus ≤ 5.5 mg/dL

6.2 Worst Toxicity CTCAE v4.03 Grade (unless otherwise specified)	6.3 Recommended Dose Modifications any time during a cycle of therapy
Serum phosphorus >7.0 – 10.0 mg/dL despite phosphate lowering therapy Serum Pi > 10.0 mg/dL	
 • if resolved by ≤ 14 days after suspending BGJ398 (infigratinib), ↓ 1 dose level • if does not resolve within 14 days of suspending BGJ398 (infigratinib), discontinue patient from the study. Discontinue patient from the study
Hypercalcemia Serum calcium grade 2 Serum calcium ≥ grade 3	Hold BGJ398 (infigratinib) dose until resolved to grade 1 or baseline: 
 • if resolved ≤ 7 days after suspending BGJ398 (infigratinib), maintain dose level • if resolved > 7 days after suspending BGJ398 (infigratinib), ↓ 1 dose level Discontinue patient from the study
Nervous system disorders	
Neurotoxicity Grade 2 Grade ≥ 3	Omit dose of BGJ398 (infigratinib) until resolved to CTCAE Grade ≤ 1, then ↓ 1 dose level of BGJ398 (infigratinib) Discontinue patient from study drug treatment
GI disorders	
Pancreatitis Grade ≥ 2	Discontinue patient from study drug treatment

6.2 Worst Toxicity CTCAE v4.03 Grade (unless otherwise specified)	6.3 Recommended Dose Modifications any time during a cycle of therapy

Diarrhea
 
Grade 1
 
Grade 2
 
Grade 3
 
Grade 4
	
Maintain dose level of BGJ398 (infigratinib), but initiate anti-diarrheal treatment
 
 • Hold dose of BGJ398 (infigratinib) until resolved to CTCAE Grade \leq 1 • Optimize anti-diarrheal treatment, maintain dose level of BGJ398 (infigratinib). • For reoccurrence of diarrhea CTCAE Grade 2, hold dose of BGJ398 (infigratinib) until resolved to CTCAE Grade \leq 1, ↓ BGJ398 (infigratinib) by 1 dose level • Hold dose of BGJ398 (infigratinib) until resolved to CTCAE Grade \leq 1 • Optimize anti-diarrheal treatment • ↓ BGJ398 (infigratinib) by 1 dose level • For reoccurrence of diarrhea CTCAE Grade 3, despite optimal anti-diarrheal treatment, discontinue patient from study treatment. 
Discontinue patient from study treatment.
 
Note: Antidiarrheal medication is recommended at the first sign of abdominal cramping, loose stools or overt diarrhea

Vomiting
 
Grade 2 not controlled by optimal anti-emetic therapy
 
Grade 3 not controlled by optimal anti-emetic therapy or Grade 4
	
Hold BGJ398 (infigratinib) doses until \leq grade 1, ↓ 1 level
 
Discontinue patient from study

Eye Disorders (confirmed by ophthalmologic examination)	

Retinal disorders
 
Grade 2 CSR and CSR-like events
 
Grade 3 CSR and CSR-like events and any other grade 3 eye disorders
	
Hold BGJ398 (infigratinib) until resolved to \leq grade 1 but refer the patient to a retinal specialist for evaluation
 
 • If resolved in \leq 14 days, ↓ BGJ398 (infigratinib) by 1 dose level • If resolved in $>$ 14 days, discontinue BGJ398 (infigratinib) 
Hold BGJ398 (infigratinib) until resolved to grade \leq 1.
 
 • If resolved in \leq 14 days, ↓ BGJ398 (infigratinib) by 1 dose level • If resolved in $>$ 14 days, discontinue BGJ398 (infigratinib)

6.2 Worst Toxicity CTCAE v4.03 Grade (unless otherwise specified)	6.3 Recommended Dose Modifications any time during a cycle of therapy
≥ grade 1 retinal vein occlusion, grade 4 CSR and CSR-like events, and grade 4 other eye disorders	Discontinue BGJ398 (infigratinib)
Other ocular/visual toxicity ≥ grade 3	Hold BGJ398 (infigratinib) until resolution to ≤ grade 1 If resolution in ≤14 days, ↓ 1 dose level, otherwise discontinue BGJ398 (infigratinib)
General disorders	
Fatigue Grade 3	Hold dose of BGJ398 (infigratinib) until resolved to CTCAE Grade ≤ 1 
 • If resolved in ≤ 7 days, maintain dose level of BGJ398 (infigratinib). • If resolved in > 7 days, discontinue patient from study treatment.
Other clinically significant AEs	
Grade 3	Hold dose of BGJ398 (infigratinib) until resolved to CTCAE Grade ≤ 1, then ↓ 1 dose level of BGJ398 (infigratinib).
Grade 4	Discontinue patient from study treatment.
All dose modifications should be based on the worst preceding toxicity. Once a dose has been reduced it will not be increased at a later time even if there is no toxicity. Patients who require more than two dose reductions of BGJ398 (infigratinib) will be discontinued from study drug treatment. If a patient requires a dose delay of > 14 days from the intended day of the next scheduled dose of BGJ398 (infigratinib) then study treatment must be stopped.	

Table 6-4 Toxicity – Follow-up evaluation

TOXICITY	FOLLOW-UP EVALUATION
Metabolic (hyperphosphatemia)	
Serum phosphorus lowering therapy consisting of dietary phosphate intake restriction and oral phosphate binders should be applied as follows:
 
Calcium-containing phosphate binders are not recommended.
 
Starting Cycle 1 Day 1 (beginning with the midday or evening meal on C1D1):
 
 - Restriction of dietary phosphate intake to 600 - 800 mg/day, if BMI ≥ 21kg/m². - Sevelamer 1 tablet (800mg) per meal; i.e. 3 x 800 mg/day.

TOXICITY	FOLLOW-UP EVALUATION
Renal	
Serum Pi > 5.5 – 7.0mg/dL: - Increase the dose of sevelamer up to 1200mg tid with meals
 
Serum Pi > 7.0mg – 9.0mg/dL - Increase the dose of sevelamer up to 1600mg (2 tablets per meal) tid with meals
 
If serum phosphorus increases > 7.0mg/dL despite phosphorus lowering therapy given for at least 14 days, the BGJ398 (infigratinib) dose should be held and then dose subsequently reduced. All patients will continue to be followed until resolution to serum phosphorus \leq 5.5 mg/dL or baseline or stabilization.
 
If serum creatinine CTCAE Grade \geq 1 has been demonstrated in conjunction with hyperphosphatemia, this parameter must be repeated at least weekly until resolution. 24-hour urine collection should also be obtained for total phosphate, calcium, protein and creatinine clearance within weekly intervals. Ultrasound examination of the kidneys should be performed as indicated to evaluate de-novo calcifications until resolution or stabilization of creatinine.

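### Table 6-3: the hold for Grade 1 creatinine with raised phosphorus ends at a threshold that Grade 1 already meets, and no other rule settles the release when phosphorus is 7.0 mg/dL or lower

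*Combined protocol and SAP*

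**What the plan says.** The serum creatinine lines of Table 6-3 (section 6.1.5, Investigations – Renal) give four triggers and four actions. The first trigger is "Grade 1 and Pi >5.5 mg/dL and/or tCa x Pi >55 mg²/dl² and despite phosphorus lowering therapy for at least 14 days". Its action is "Hold dose of BGJ398 (infigratinib) until resolved to CTCAE Grade ≤ 1 or baseline", with the same dose if this takes up to 7 days and one dose level lower if it takes longer. The third trigger is "Grade 2 and Pi >5.5 mg/dL and/or tCa x Pi >55 mg²/dl² and despite phosphorus lowering therapy for at least 14 days", and its action is discontinuation.

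Other rules that bear on the point:

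- **Section 6.1.5, general text.** Treatment restarts once the toxicity is at baseline or at Grade 1 or lower, at the dose that Table 6-3 sets. If it restarts at the same dose "and the same toxicity recurs with the same or worse severity regardless of duration, doses must be reduced to the next lower dose level". Also: "All dose modifications should be based on the worst preceding toxicity".
- **Table 6-3, hyperphosphatemia row.** For Pi above 5.5 and up to 7.0 mg/dL, the dose is kept and phosphate-lowering therapy is adjusted. For Pi above 7.0 and up to 10.0 despite therapy, drug is held until Pi is 5.5 or lower, then reduced one level if that happens within 14 days. Above 10.0, the patient stops.
- **Table 6-3, closing note.** "Once a dose has been reduced it will not be increased at a later time even if there is no toxicity". A dose delay longer than 14 days ends treatment.
- **Table 6-4.** Phosphorus-lowering therapy begins at study start: "Starting Cycle 1 Day 1 (beginning with the midday or evening meal on C1D1". Creatinine of Grade 1 or higher with hyperphosphatemia is rechecked at least weekly.

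**The concern.** A hold needs a release that is not yet met when the hold starts. Here the hold is triggered by Grade 1 creatinine together with a phosphorus abnormality, but the release looks only at creatinine and accepts Grade 1. The abnormality that turns a Grade 1 value into a reason to hold plays no part in restarting.

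The stake is consistent handling of a safety rule. Within the renal row this is the only step before mandatory discontinuation under the same phosphorus condition (the Grade 2 line with raised Pi or product). Section 1.2.1.1.2 reports raised phosphorus with kidney mineralization in animals, so it matters whether patients in this state stay on drug while the abnormality persists.

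**Working it through.** No sample size or error rate is involved. The check sets the trigger against the release, looks for another rule that would settle it, and then sizes the difference.

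**1. Pairing in the renal row**

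| Trigger | Action | Release already met at trigger? |
|---|---|---|
| Grade 1 + Pi/product condition | Hold to Grade ≤ 1 or baseline | Yes: 1 ≤ 1 |
| Grade 2 | Hold to Grade ≤ 1 or baseline | No: 2 > 1 |
| Grade 2 + Pi/product condition | Discontinue | – |
| Grade ≥ 3 | Discontinue | – |

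Four triggers match four actions in order, so this does not look like a text-extraction fault. Exclusion 17 (section 5.2) requires entry creatinine below the upper limit of normal, so baseline would normally be the stricter target. Because the two release conditions are joined by *or*, Grade 1 is enough. In the other holds of Table 6-3 the trigger does not already meet the release. For example, Grade 3 amylase or lipase is released at Grade 2 or lower, and Grade 2 hypercalcemia at Grade 1 or baseline.

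**2. Other rules**

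- The general restart rule in section 6.1.5 uses the same threshold and refers back to Table 6-3.
- The hyperphosphatemia row has a Pi-based release only for its own hold, above 7.0 mg/dL.
- Table 6-4 also holds only above 7.0. Its Pi endpoint of 5.5 and its weekly creatinine are follow-up, not restart conditions.
- The recurrence rule and the 14-day limit act after the initial hold and do not define its end.

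Nothing settles the release for Pi above 5.5 and up to 7.0, or for Pi at or below 5.5 with the product above 55.

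**3. Size in cycle 1**

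Therapy starts on C1D1, so the earliest trigger day is C1D15. Doses left: 21 − 15 + 1 = 7, and 7/21 = 33%.

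| Reading | Doses taken | Cycle 1 total |
|---|---|---|
| Zero-day hold | 21 | 21 × 125 = 2625 mg |
| Hold until creatinine is at baseline | as few as 14 | 14 × 125 = 1750 mg |
| Hold until Pi and product are within limits | as few as 14 | 14 × 125 = 1750 mg |

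Seven doses is a ceiling. It needs the trigger to be acted on before the C1D15 dose and no release before day 21. Dosing is in the morning (section 6.1.2) and binders start at a later meal on C1D1. If the day 15 dose is already taken, at most 6 doses are at issue (6/21 = 29%; 15 × 125 = 1875 mg). Days 22–28 are off drug on every reading.

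**4. After cycle 1**

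On the second and third readings, recovery in more than 7 days means 100 mg: (125 − 100)/125 = 20% lower, without later re-escalation. The zero-day reading may also reach 100 mg through the recurrence rule. The text does not say whether an unchanged value at the next weekly check counts as a recurrence.

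**5. What a corrected release must contain**

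A Pi limit alone is not enough. At Pi 5.5 the product still exceeds 55 if total calcium is above 55/5.5 = 10.0 mg/dL. At Pi 7.0 it does so above 55/7.0 = 7.86 mg/dL.

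Precedence above 7.0 also has to be stated. Take Grade 1 creatinine with Pi 8.0 despite at least 14 days of therapy, with Pi and product back within limits in 5 days. A release with only the 7-day rule would keep 125 mg, while the hyperphosphatemia row requires 100 mg.

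**The case against.** The strongest reply is that a zero-day hold empties the instruction of meaning, so a sensible site would read the hold as lasting until the combined abnormality ends: phosphorus back within limits, creatinine allowed at Grade 1. That is a natural reading, and probably a likelier one than the literal reading. But the text does not state it, and a hold to baseline creatinine is also defensible. Those two can give different hold lengths and different doses on restart.

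Existing safeguards also count: weekly creatinine, urine collection and renal ultrasound as indicated (Table 6-4), binder escalation, the separate hold above Pi 7.0, the recurrence reduction, discontinuation at Grade 2 with raised phosphorus, and weekly safety teleconferences (section 13.5). Section 1.2.1.2.3 describes the increases in patients as generally mild to moderate, reversible and without clinical symptoms. These limit the risk, but they do not define when the hold ends. Table 6-3 is titled as recommended modifications, yet section 6.1.5 introduces its guidelines as ones that need to be applied.

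Three stronger inferences are tempting, and the documents do not support them:

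- *The line has no effect on dosing.* Sites may hold on either of the other readings, and the recurrence rule may force a reduction.
- *No restart rule exists elsewhere.* Section 6.1.5 has one. It repeats the threshold and so does not settle the matter.
- *Many patients are affected, or the response analysis is.* The component events are common (hyperphosphatemia 65.4% and creatinine increase 29.8% in the first-in-human study, section 1.2.1.2.1), but the documents give no rate for this combined trigger and show no route to the primary result.

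**Conclusion.** The release for this one line fails as written and should be corrected. It is a wording fault in a safety rule: for Pi at or below 7.0 mg/dL the protocol supports three readings, and sites with the same laboratory values can dose or hold. The cycle 1 difference is at most 7 of 21 doses per affected patient, and the readings may later converge at 100 mg. No patient count can be given.

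The conclusion assumes that triggers and actions pair in the printed order, and that a Grade 1 creatinine is not the patient's baseline value, which exclusion 17 makes the normal case. The Grade 2 creatinine hold is sound.

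**What to change.** For the Grade 1 line only, replace the release with:

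> Hold until (Pi ≤ 5.5 mg/dL and tCa x Pi ≤ 55 mg²/dL²) or creatinine is below Grade 1 or at baseline. If met in ≤ 7 days, maintain dose level; if met in > 7 days, ↓ 1 dose level. If Pi was > 7.0 mg/dL despite phosphate-lowering therapy, the hyperphosphatemia row also applies and the stricter action governs (hold until Pi ≤ 5.5, then ↓ 1 dose level).

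While creatinine stays at Grade 1 (and above baseline) and either phosphorus limit is exceeded, this release cannot be met. The *or* keeps it consistent with the hyperphosphatemia row: once creatinine is below Grade 1, Pi above 5.5 and up to 7.0 alone is a keep-dose state. Discontinuation above Pi 10.0 is unchanged.

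The change is to one table cell. It needs no new tests: the trigger already uses all three values, and weekly follow-up after an interruption is already required (section 6.4). Compared with the literal reading it brings longer holds, some added dose reductions, and possibly a few discontinuations at the 14-day limit. For a hold starting on C1D15, 15 + 14 = study day 29, which is C2D1 (section 4.4), so the release must be met by then. Section 6.1.5 allows an exception with the manufacturer's approval.
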